- Adherence to current guidelines on the management of acute pulmonary embolism released by the European Society of Cardiology concerning diagnosis, risk stratification, hospitalization and treatment. These items will be evaluated in the overall study population and compared between patients admitted in every-day clinical practice in Cardiology, Emergency or Internal Medicine Departments.

Primary study outcome

The co-primary study outcomes are

- in-hospital death and
- death at 30 days from the diagnosis of pulmonary embolism.

Secondary study outcomes

The secondary study outcome are:

- death or clinical deterioration at 30 days from the diagnosis of pulmonary embolism.
- pulmonary embolism-related death or clinical deterioration at 30 days from the diagnosis of pulmonary embolism
- Adherence to current guidelines on the management of acute pulmonary embolism released by the European Society of Cardiology regarding diagnosis, risk stratification and treatment.

For all patients, the cause of death will be reported as assessed by the attending physician and classified as:

- Unexpected
- Pulmonary-embolism related
- Due to bleeding
- Due to cardiovascular events other than pulmonary embolism
- Due to cancer
- Other non-cardiovascular causes

Pulmonary embolism-related death is defined as i) death where pulmonary embolism is the most probable cause or ii) based on objective diagnostic testing performed before death or iii) as assessed at autopsy (autopsy is not mandatory).

Documentation on study outcome events (in-hospital and 30 day deaths) will be centrally collected in order to allow an independent adjudication committee to definitely adjudicate the cause of death.

Clinical deterioration is defined as the occurrence of at least 1 of the following (25):

- (iv) the need for cardiopulmonary resuscitation;
- (v) systolic blood pressure <90 mm Hg for at least 15 minutes, or drop of systolic blood pressure by at least 40 mm Hg for at least 15 minutes, with signs of end-organ hypoperfusion (cold extremities, or urinary output <30 mL/h, or mental confusion);
- (vi) the need for catecholamine infusion (except for dopamine at a rate of <math><5 \mu\text{g kg}^{-1} \text{min}^{-1}</math>) to maintain adequate organ perfusion and a systolic blood pressure of >90 mm Hg.

Adherence to ESC guidelines 2014 will be assessed concerning:

- diagnosis
- risk stratification
- treatment

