- global management (the composite of diagnosis, risk stratification and treatment)

Six process indicators were selected, based on recommendations from ESC guidelines (6). The indicators are:

- (1) Time from diagnosis to initiation of anticoagulant treatment. The time of CT angiography or of lower limbs ultrasonography will be considered as time of diagnosis.
- (2) Number of diagnostic tests applied and their order within the diagnostic work-up based on estimated pre-test probability of pulmonary embolism.
- (3) Type, number and timing (within 24 hours) of tests performed for prognostic assessment.
- (4) Use of systemic thrombolysis or percutaneous manoeuvre associated with intravenous heparin for at least 48 hours in hemodynamically unstable patients.
- (5) home treatment or short hospital stay (<48 hours) in patients with low-risk pulmonary embolism
- (6) The number, dose and sequence of antithrombotic agents according to currently validated regimens.

Safety Objective

The safety objective of this study is to collect and evaluate real-world safety data on bleeding events in patients with acute pulmonary embolism.

Safety Outcomes

The primary safety outcome is:

- Major bleeding according to ISTH definition, occurring up to 30 days from the diagnosis of index pulmonary embolism.

Major bleeding, defined (as per ISTH guidelines), as acute clinically overt bleeding (i.e. bleeding that is visualized by examination or radiologic imaging) associated with one or more of the following:

- decrease in hemoglobin of 2 g/dl (1.2 mmol/L) or more;
- transfusion of 2 or more units of packed red blood cells;
- bleeding that occurs in at least one critical site [intracranial, intra-spinal, intraocular (within the corpus of the eye; thus, a conjunctival bleed is not an intraocular bleed), pericardial, intra-articular, intramuscular with compartment syndrome, or retroperitoneal];
- bleeding that is fatal;
- bleeding that necessitates acute surgical intervention

Major bleeding events will also be further sub-classified as life-threatening or non-life threatening. A life-threatening major bleed is defined as a bleeding event that is either intracranial or is associated with haemodynamic compromise requiring intervention.

The secondary safety outcome is:

- Clinically relevant non-major bleeding.

Clinically relevant non-major bleeding event defined as acute clinically overt bleeding that does not meet the criteria for major and consists of:

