- any bleeding compromising hemodynamics;
- spontaneous hematoma larger than 25 cm², or 100 cm² if there was a traumatic cause;
- intramuscular hematoma documented by ultrasonography;
- epistaxis or gingival bleeding requiring tamponade or other medical intervention or bleeding from venipuncture for >5 minutes;
- hematuria that was macroscopic and was spontaneous or lasted for more than 24 hours after invasive procedures;
- hemoptysis, hematemesis or spontaneous rectal bleeding requiring endoscopy or other medical intervention;
- or any other bleeding considered to have clinical consequences for a patient such as medical intervention, the need for unscheduled contact (visit or telephone call) with a physician, or temporary cessation of a study drug, or associated with pain or impairment of activities of daily life.

STUDY PROCEDURES

Patient information and informed consent

Before being admitted to the study, the subject must consent to participate after full information about the nature, scope, and possible consequences of the study.

The documents must be in a language understandable to the subject and must specify who informed the subject. A copy of the signed informed consent document must be given to the subject. The original signed consent document will be retained by the investigator.

Moreover, a letter will be provided to every patient to inform his/her primary physician about the subject's participation in the study - provided the subject agrees to the primary physician being informed.

After reading the informed consent document, the subject must give consent in writing.

No personal patient's contact details (like mobile phone number) will be recorded in the study database.

Visits schedule and follow-up

Patients will be evaluated at the time of diagnosis of pulmonary embolism (baseline), at discharge (FU 1) and at 30 days (± 4) from index pulmonary embolism (FU 2).

For some patients, discharge may occur beyond 30 days from index pulmonary embolism. These patients will have two study assessments only (baseline and 30 days).

At baseline, patient status at presentation (hemodynamics, respiratory failure, etc.), the relevant patient history (including concomitant medications), diagnostic strategies and assessments for risk stratification will be recorded.

Telephone call is allowed for the 30-day follow-up using standardized interview (Appendix 1).

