The following data will be collected at baseline for all enrolled patients:

- Demographics i.e. Age, Gender, pregnancy or lactation
- Vital Signs i.e. Blood pressure, Heart rate, oxygen saturation in room air, saturation in oxygen, respiratory rate, hourly urinary output, Height, Weight
- Medical History (past and current status) i.e. o Relevant comorbidities present at baseline (e.g. cancer, COPD, diabetes, dyslipidemia, previous major bleedings), recent history (recent trauma or hospitalization or surgery)
- Pulmonary embolism, Diagnosis and Interventions (past and current status) i.e. o Type of past VTE (DVT or/and PE, first or recurrent), date of diagnosis, symptoms at diagnosis, etc. ; diagnostic work-out,
- Risk stratification i.e. echocardiography, clinical models, cardiac evaluation at CT angiography
- Anticoagulant treatment (agents, time of initiation, dose, duration)
- Concomitant CV and non CV treatments, including non-pharmacological treatments
- Laboratory examinations i.e. renal function, hemoglobin, cardiac enzymes.
- Other VTE-relevant patient information e.g. Bleeding disposition, Thrombocytopenia, Alcohol consumption, frailty
- Hospitalisations related to current pulmonary embolism i.e. Emergency Room, Intense Care Unit, Cardiology, Internal Medicine .

Study visit at discharge

The following data are planned to be collected at discharge:

- Date of documentation
- Vital status and Current vital signs i.e. dead/alive
- Clinical deterioration, bleeding during the hospital stay i.e. date, treatment strategies
- Anticoagulant treatment during the hospital stay i.e. agent, dose, initiation/stop date,
- Anticoagulant treatment at discharge i.e. agent, dose, initiation/stop date,
- concomitant CV and non CV treatments

Study visit at 30 days

The following data are planned to be collected at discharge:

- Date of documentation
- Vital status and Current vital signs i.e. dead/alive
- Clinical deterioration, bleeding during the hospital stay i.e. date, treatment strategies
- Anticoagulant treatment during the hospital stay i.e. agent, dose, initiation/stop date,
- Anticoagulant treatment at discharge i.e. agent, dose, initiation/stop date,
-concomitant CV and non CV treatments, including non-pharmacological treatments
- Follow-up examinations i.e. laboratories (renal function, hemoglobin, cardiac enzymes), cardiac (EKG, echocardiography, CT).
- Hospitalisations i.e. related to index pulmonary embolism or other causes
- Adverse drug reactions

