Data from routine patient data collection points or telephone interviews at the respective site should be documented directly in the Medical Records and entered shortly thereafter into the eCRF.

Early Study Termination

In case a patient terminates the study early, reason for early study termination (lost to follow-up, investigator's decision, adverse events, withdrawal of consent etc.) will be recorded.

The treating physician should at least get awareness of the patient's vital status at the time of the early termination of patient participation in the study.

Withdrawal of Consent

In accordance with the Declaration of Helsinki and other applicable regulations, a patient has the right to withdraw consent for participation in the study at any time and for any reason without prejudice to his or her future medical care by the physician or at the institution.

If a patient withdraws consent to participate in the study, the investigator will complete and report the observations as thoroughly as possible up to the date of consent withdrawal and including the date of the final contact with the patient. The investigator will clearly document the reason (if given) for consent withdrawal in the medical record and will complete the associated electronic case report form (eCRF) section.

Data Management

An electronic CRF system will be used for data capture.

A data management plan will be created in the study start phase and will describe all functions, processes, and specifications for data collection, cleaning and validation. The eCRFs will include automated plausibility checks (e.g. range checks, conditional checks, etc.) at data entry to obtain immediate feedback if data are missing, out of range, illogical or potentially erroneous and allow for correction or confirmation by the site. Concurrent manual data review will be performed based on parameters defined in the data management plan. If necessary, queries will be manually generated within the eCRF system and followed up for resolution.

Critical fields will be defined that need to be filled in by the site prior to signing the eCRF.

Data Entry/Electronic Data Capture

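### The 30-day outcomes are not fully secured: last contact may be on day 26, the 30-day data list repeats the discharge wording, and early leavers need only vital status at exit

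*Protocol*

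**What the plan says.** **Outcomes.** Under Primary study outcome, one co-primary is "death at 30 days from the diagnosis of pulmonary embolism". Secondary study outcomes include "death or clinical deterioration at 30 days from the diagnosis of pulmonary embolism" and the same composite restricted to embolism-related death. Under Safety Outcomes, the primary one is "Major bleeding according to ISTH definition, occurring up to 30 days from the diagnosis of index pulmonary embolism".

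**Timing of the last contact.** Visits schedule and follow-up places it "at 30 days (± 4) from index pulmonary embolism (FU 2"). The Study schedule table gives the same window, and its footnotes (e) and (h) label the contact as a four-week one.

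**Content of the last contact.** In Observations and measurements, the list headed Study visit at 30 days opens with "The following data are planned to be collected at discharge", the same sentence that opens the discharge list. It then gives "Clinical deterioration, bleeding during the hospital stay i.e. date, treatment strategies", again identical to the discharge list, followed by anticoagulant treatment during the stay and at discharge. The same list also has dead/alive status, follow-up examinations, hospital admissions whatever their cause, and adverse drug reactions. The Study schedule table marks assessment of death, deterioration and bleeding at the 30-day visit, and footnote (h) lets the telephone query cover the efficacy and safety endpoints.

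**Early leavers.** Early Study Termination asks the physician to learn, as a minimum, the patient's "vital status at the time of the early termination of patient participation in the study".

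**Analysis.** Statistical methodology plans logistic models, Kaplan-Meier plots and Cox models. Analysis of primary endpoint reports the overall rate of death at 30 days with a confidence interval.

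**The concern.** An outcome defined at day 30 needs each patient's status to be known through day 30. Three provisions fall short of that.

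1. A site that makes its final contact on days 26-29 has met the protocol, yet the remaining days up to day 30 are unseen.
2. An eCRF page built from the 30-day list would have no dedicated field for deterioration, bleeding or anticoagulant changes after discharge.
3. A patient who leaves early and is alive at exit has an unknown day-30 status, and nothing requires it to be sought.

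All three push towards undercounting. The first and third touch 30-day death, which is co-primary. The first and second touch the deterioration composites and major bleeding. The second matters most where the hospital stay is short. Process indicator 5 treats home care or a stay under 48 hours as guideline-adherent for low-risk patients, who are the largest planned stratum (2,500 of 5,000). For a patient managed that way, at least 30 − 2 = 28 of the 30 days lie after discharge.

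**Working it through.** **Step 1. Expected deaths (inputs from Sample Size).**

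- Intermediate risk: 2,100 × 3% = 63
- Low risk: 2,500 × 0.5% = 12.5
- High risk: 400 × 10% to 15% = 40 to 60
- Total: 63 + 12.5 + (40 to 60) = **115.5 to 135.5** in 5,000 patients, or 2.31% to 2.71%

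The protocol's own figure is about 100 deaths, which these inputs do not reproduce. That is a separate matter. The computed range is used below.

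**Step 2. The window.** Day 30 − 4 = day 26 and day 30 + 4 = day 34. After a day-26 contact, days 27-30 are unobserved. The protocol gives neither the timing of deaths nor the distribution of contact days, so both are assumed.

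| Share of 30-day deaths on days 27-30 | Deaths in those days |
|---|---|
| 3% | 115.5 × 0.03 = 3.5 to 135.5 × 0.03 = 4.1 |
| 8% | 115.5 × 0.08 = 9.2 to 135.5 × 0.08 = 10.8 |

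So about **3 to 11** deaths would be missed if every patient were last contacted on day 26. If a quarter were, the figure is 3.5 × 0.25 = 0.9 to 10.8 × 0.25 = 2.7.

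As a check on the 3-8% range, a Weibull-type decline gives a share of 1 − (26/30)^k, which is 6.9% for k = 0.5 and 4.2% for k = 0.3. Both lie inside it. Deaths spread evenly over the month would give 4/30 = 13.3%, or 15.4 to 18.1 deaths with every contact on day 26. That is the outer case.

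**Step 3. Early leavers.** Number = 5,000 × exit proportion (assumed). Deaths = number × 2.31% to 2.71%.

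| Exit proportion | Patients | Deaths over the full 30 days |
|---|---|---|
| 1% | 50 | 1.2 to 1.4 |
| 2% | 100 | 2.3 to 2.7 |
| 5% | 250 | 5.8 to 6.8 |

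These figures assume average risk. They cover the whole 30 days, so at that risk the deaths after exit are fewer.

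**Step 4. The data list, by comparison of sections.**

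| Item at 30 days | Outcome sections | Study schedule table | Study visit at 30 days list |
|---|---|---|---|
| Death | to day 30 | assessed | dead/alive, no restriction |
| Deterioration | to day 30 | assessed | hospital stay only |
| Bleeding | to day 30 | assessed | hospital stay only |
| Anticoagulant treatment | not an outcome | no row of its own after enrolment | hospital stay and discharge only |

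The conflict is confined to deterioration, bleeding and treatment data. The protocol gives no expected rates for deterioration or bleeding, so this part cannot be sized.

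**Step 5. Which analyses are affected.** Kaplan-Meier and Cox analyses can censor a patient at the last contact. A crude 30-day proportion or a logistic model needs a yes or no at day 30. A patient last seen alive on day 26 would be counted as event-free without observation, unless excluded.

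**The case against.** The best defence is that the protocol does provide for outcome assessment at 30 days. The Study schedule table marks all three outcome components at that visit, footnote (h) extends the telephone query to efficacy and safety endpoints, and the section says that scheduled assessments are those in the table. The 30-day list looks like text carried over from the discharge list. The telephone call follows a standardised interview in Appendix 1, whose content is not in the text available for review, so what it asks cannot be judged. The ± 4 day window is symmetric and of an ordinary kind, the list records a date of documentation, and survival methods handle early contact. The early-termination rule sets a floor and does not bar later follow-up.

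Most of this stands, and it rules out two stronger readings. A reader might infer that the 30-day visit cannot deliver the 30-day outcomes, or that its list covers only the hospital stay. Neither is supported: the schedule provides for the outcomes, and the list includes vital status, admissions for any cause, follow-up examinations and adverse drug reactions without restriction to the stay.

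The defence does not remove three things. The list and the schedule disagree and an eCRF designer could follow either. No provision requires status to be confirmed through day 30. The crude rates and the logistic models, which are the stated basis of the sample size, have no censoring to fall back on.

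**Conclusion.** The point holds in a limited form: the 30-day outcomes are provided for but not fully secured. The list for the 30-day visit contradicts the outcome definitions and the schedule table on deterioration and bleeding, and these must be reconciled. Separately, neither the window nor the early-termination rule guarantees vital status at day 30.

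The effect on deaths is modest. At most about 3 to 11 of 115.5 to 135.5 expected deaths would be missed through the window, if 3-8% fall on days 27-30 and every patient is contacted on day 26. Both conditions are assumptions, and the second is extreme. Early exit of 2% (assumed) at average risk adds about 2 to 3 deaths.

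A reader might set 100 patients of unknown status against some 116 to 136 deaths and conclude that the result is swamped. That compares patients with events, and at the protocol's own mortality those 100 carry 2 to 3 deaths. Nor does the protocol say that low-risk patients leave within 48 hours; that is an adherence measure the study will observe. Low-risk patients contribute only 12.5 of the expected deaths. With mortality of 2.3% to 2.7%, however, small losses still merit a cheap correction.

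**What to change.** 1. **Window.** Let the final contact open at day 30, for example day 30 to day 38, and count only events dated up to day 30. Align the four-week labels in the schedule footnotes.
2. **30-day list.** Correct its opening line, and reword the deterioration, bleeding and anticoagulant items to cover the period since discharge, or since baseline for patients still in hospital. This brings the list into line with the Study schedule table and footnote (h).
3. **Early leavers.** For those who have not withdrawn consent, seek vital status at day 30 from clinical records or through the telephone contact already agreed to. The primary physician should not be assumed as a source: the information letter depends on the patient's agreement, and the stated data sources are clinical records and telephone interviews. That route could need more than a wording change.

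**Cost.** Protocol and eCRF wording, with the same number of contacts. Some calls are made a few days later; the latest would be 38 − 34 = 4 days after the present limit. Item 3 adds a small amount of site work for the few patients concerned.

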The Table outlines the data to be collected at different timings. The data sources used in this study are clinical records, and data from telephone interviews.

The patient is asked within the ICF, whether he/she is willing to get contacted by the treating physician for standardized telephone interviews and needs to agree to provide contact details as long this procedure is in line with the clinical practice

Table: Study schedule

	Visit 1	Visit 2	Visit 3
	Enrollment	Discharge	30-days
			from diagnosis (± 4 days)
Informed consent	x		
Demography	x		
Medical History	x		
Pulmonary embolism Diagnosis (a)	x		
Physical Examination	x		x
Vital Signs (b)	x	x	x
Serum chemistry (c)	x		x
Hematology	x (d)		x (e)
Eligibility criteria	x		
Inclusion/Exclusion criteria	x		
Risk stratification procedures (f)	x	x	
Hospitalization (g)	x	x	
Assess study outcomes (i.e. death, clinical deterioration, bleeding) (h)		x	x
Prior and Concomitant Medications	x		

- (a) i.e. Symptoms of pulmonary embolism, number and sequence of confirmatory tests
- (b) i.e. Blood pressure, Heart Rate, Oxygen saturation, Respiratory rate, urinary output.
- (c) i.e. Total Bilirubin (Direct and Indirect), ALT, AST, ALP, Serum creatinine, Creatinine clearance (Cockcroft Gault equation)
- (d) At enrollment: Hematocrit, WBC, Hb, Plts, INR, PTT, d-dimer, etc
- (e) At enrollment and 4-wks: Hematocrit, WBC, Hb, Plts, etc
- (f) i.e. echocardiography, cardiac enzymes, assessment at CT angiography.
- (g) i.e. home-treatment or hospitalization, department of hospitalization
- (h) at 4-wks telephone query of health status (alive, occurrence of efficacy and safety endpoints and AEs/SAEs) is allowed. Subjects who have new symptoms should undergo further assessment as clinically appropriate, preferably at the study site whenever feasible.

Observations and measurements

Scheduled assessments for the study are presented in the Study schedule Table. All data will be collected from information routinely recorded in the patient files/medical records or during telephone follow-up interviews. All these data are available as part of the routine treatment. All examinations performed depend on the discretion and clinical routine of the physician. No diagnostic or monitoring procedures and no examinations, laboratory tests or procedures are applied to the patients as part of this non-interventional study others than those performed as standard of care.

Baseline/Enrolment

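### The 30-day visit list repeats the discharge item limiting bleeding and clinical deterioration to the hospital stay, against the 30-day outcome windows and the schedule table

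*Protocol*

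**What the plan says.** **Outcome definitions.** Under Safety Outcomes, the primary safety outcome is "Major bleeding according to ISTH definition, occurring up to 30 days from the diagnosis of index pulmonary embolism". Under Secondary study outcomes, the two clinical composites are "death or clinical deterioration at 30 days from the diagnosis of pulmonary embolism" and "pulmonary embolism-related death or clinical deterioration at 30 days from the diagnosis of pulmonary embolism". All three have a 30-day window counted from diagnosis.

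**Schedule.** The study schedule table has a row "Assess study outcomes (i.e. death, clinical deterioration, bleeding) (h", marked at discharge and at the 30-day visit, with no restriction to the hospital stay. Its footnote (h) adds: "at 4-wks telephone query of health status (alive, occurrence of efficacy and safety endpoints and AEs/SAEs) is allowed".

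**Data lists.** Observations and measurements opens by pointing back to that table: "Scheduled assessments for the study are presented in the Study schedule Table". It then itemises the data visit by visit. Under Study visit at 30 days the lead-in is "The following data are planned to be collected at discharge", and the outcome item is "Clinical deterioration, bleeding during the hospital stay i.e. date, treatment strategies". Lead-in and item are both identical to those under Study visit at discharge. The two anticoagulant items (in-hospital and at discharge) are repeated as well. The 30-day list does have entries of its own: follow-up examinations, hospitalisations for any cause, and adverse drug reactions.

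**The concern.** The table names the outcome domains. The visit list is the itemised text, and the only one of the two that asks for the date and treatment of each event. Someone building or completing the eCRF from the list would ask at day 30 about the hospital stay only. From the table, they would ask about the full 30 days.

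Under the list's wording, the time during which a non-fatal event can be recorded equals length of stay. A patient who goes home early and bleeds or deteriorates later would be counted as event-free to day 30, because vital status at day 30 is known and the patient stays in the denominator.

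Length of stay is tied to what the study compares. Home treatment or a stay under 48 hours in low-risk patients is one of the six adherence indicators, and adherence is to be examined as a predictor of death or clinical deterioration. Short stay could then look safer merely because there was less time in which to record an event. Comparisons by risk class and by department would be exposed in the same way wherever stay differs between groups.

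**Working it through.** No figure in the protocol needs reproducing, so the check sets the texts side by side.

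| Place in the protocol | Window for major bleeding | Window for clinical deterioration |
|---|---|---|
| Safety Outcomes; Secondary study outcomes | diagnosis to day 30 | diagnosis to day 30 (within the composites) |
| Study schedule table and footnote (h) | assessed at discharge and at day 30, no limit to the stay | same |
| Study visit at discharge | hospital stay | hospital stay |
| Study visit at 30 days | hospital stay | hospital stay |

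1. *Is this a real conflict?* Yes. The last row disagrees with the first two. For a patient discharged before day 30, it adds nothing to the discharge row.

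2. *Is it a carry-over?* Very probably. The 30-day lead-in refers to discharge, and the outcome and anticoagulant items repeat the discharge list. The definitions, the table and footnote (h) agree with one another, so the intended window is clear and the list is the text in error.

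3. *What would be lost if the list were followed?*
   - Deaths: nothing. Vital status at day 30 is collected without restriction, and the cause of in-hospital and 30-day deaths is centrally adjudicated.
   - Composites: only clinical deterioration after discharge in patients who do not die by day 30.
   - Major bleeding: non-fatal events after discharge.
   - Clinically relevant non-major bleeding: events after discharge, including those that led only to an unscheduled visit or telephone call, which the definition counts.
   - Co-primary outcomes: unaffected, since both are deaths.

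4. *Would other items recover these events?* In part. Hospitalisations, adverse drug reactions and follow-up haemoglobin could reveal some. They do not ask for transfusion, critical site or surgical intervention, and they would miss bleeds managed by telephone. Central adjudication covers cause of death only. On-site source checks cover consent and a limited set of variables.

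5. *Does the analysis need the missing detail?* Yes. Analysis of secondary endpoints plans Kaplan-Meier estimates for both composites and Cox models for the secondary endpoints. These need event dates, and the only itemised request for the date of a bleed or deterioration is the one limited to the stay.

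6. *Can the loss be sized?* No. The protocol gives no rate of bleeding or deterioration after discharge, no distribution of length of stay and no share of patients treated at home.

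**The case against.** The strongest reply is that collection at day 30 is already provided for. The section containing the list defers to the schedule table for the scheduled assessments, the table marks these outcomes at day 30, and footnote (h) has the 4-week call ask about efficacy and safety endpoints. The slip is visible, since a 30-day list that says its data are collected at discharge is unlikely to be built literally. The instruments that decide the matter, the eCRF and the Appendix 1 interview, are not in the text available for review, and that absence is no fault of the plan. All of this stands. It reduces the point to an internal contradiction with a conditional consequence.

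It does not remove the contradiction. The table shows the intended window without specifying the event details, and the list specifies the details with the wrong window.

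A reader might infer three stronger things that the protocol does not support:

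- *That post-discharge events drop out of the outcomes.* The table and footnote provide for their assessment, so non-collection is not shown.
- *That both composites become in-hospital outcomes.* Deaths to day 30 remain in them even on the literal reading.
- *That most of the information is lost.* For a stay of 2 days, (30 − 2)/30 = 93% of the calendar days fall outside the item, and low-risk patients are 2500 of the 2100 + 2500 + 400 = 5000 planned. But days are not events, and early risk may well differ from later risk. How many low-risk patients have a short stay is something the study sets out to measure.

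**Conclusion.** The 30-day visit list contradicts the protocol's own outcome windows and schedule table for bleeding and clinical deterioration, and should be reconciled with them. The contradiction follows from the text alone and rests on no assumption.

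The consequence is conditional. If the eCRF followed the list, non-fatal bleeding and deterioration after discharge, with their dates, could be under-recorded, more so the shorter the stay. The bias would favour groups with short stay or home treatment in comparisons by risk class, department and adherence. Its size cannot be computed from the protocol. The point touches the primary safety outcome, the secondary safety outcome and one component of each clinical composite. It does not touch the co-primary outcomes.

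**What to change.** Under Study visit at 30 days, correct the lead-in so that it refers to the 30-day visit. Replace the outcome item by: clinical deterioration and bleeding from diagnosis to day 30 (including any event since the discharge assessment, and in-hospital events for patients still hospitalised at day 30), with date, treatment and the elements of the major and clinically relevant non-major bleeding definitions.

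The item should start at diagnosis. Asking only about events since discharge would miss patients still in hospital at day 30, who according to Visits schedule and follow-up have only the baseline and 30-day assessments. The date is needed for the time-to-event analyses. It also allows events after day 30 to be set aside when the contact falls late in the ±4-day window (up to day 30 + 4 = 34).

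Review the repeated anticoagulant items in the same list at the same time. Then check that the eCRF and the Appendix 1 interview ask the same questions; they may already do so.

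The cost is a protocol wording correction and, if the eCRF lacks them, a few fields. The contact already takes place, so no visit or procedure is added. The check is best made before data collection, because events not asked about at day 30 may not be recoverable later.
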